Original Article NCT03615755

Short Duration Hyperbaric Oxygen Therapy to Improve HbA1c, Leukocyte, and Serum Creatinine in Patient with Diabetic Foot Ulcer Wagner 3-4

Author:

dr. [name]

Surgery Department, Faculty of Medicine, Udayana University, Sanglah General Hospital, Denpasar, Indonesia.

Co-Author 1:

Dr. dr. [name], Sp.B, Sp.BTKV

Thorax and Cardiovascular Surgery Division, Surgery Department, Faculty of Medicine, Udayana University, Sanglah General Hospital, Denpasar, Indonesia.

Co-Author 2:

[name]. dr. [name], Sp.PD-KGH

Nephrology and Hypertension Division, Internal Medicine Department, Faculty of Medicine, Udayana University, Sanglah General Hospital, Denpasar, Indonesia.

Correspondence:

Name : dr. [name]
[contact]
Email : [contact]
Affiliation : Surgery Department, Faculty of Medicine, Udayana University, Sanglah General Hospital, Denpasar, Indonesia.
Address : [name].

Denpasar, 10-04-2018

dr. [name]

Methods

This study uses pretest and posttest control group design, to know the role of standard therapy and combination therapy (standard therapy with adjuvant HBOT) to decrease HbA1c levels, leukocyte count, and serum creatinine levels in DFU patient Wagner 3-4. All DM patients with DFU at Sanglah General Hospital, Denpasar who meet the inclusion and exclusion criteria and willing to follow the research procedure. All patients are signing the agreement paper after getting research explanation. All patients were briefed on the study research using HBOT. If they are willing to participate in the study and use HBOT was grouped to combination therapy, if they are willing to participate in the study but do not want to use HBOT was grouped to standard therapy, but if they are not willing participate then excluded. The study was approved by Institutional Review Board of Medical Faculty of Udayana University and Sanglah General Hospital Denpasar with the ethical number 580/UN.14.2/KEP/2016.

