Thirty diabetic patients with DFU Wagner 3-4 were participated in this study. All patients were taken blood test for HbA1c levels, leukocyte count, and serum creatinine levels before debridement, then grouped for standard therapy or standard therapy with 10 sessions of HBOT. One session of HBOT uses oxygen at 2.4 ATA for 90 minutes per day at multiplace hyperbaric chamber. This therapy is given five sessions in a week, so it takes two weeks. At the end of therapy, all blood tests were performed again in both groups.

The inclusion criteria were patients who had type 2 diabetes and DFU Wagner class 3 or 4, aged over 18 years, and underwent debridement with or without toe amputation. The exclusion criteria were patients who had severe organs dysfunction such as heart failure, pulmonary infection, pneumothorax, chronic obstructive pulmonary disease, and stroke.

Statistical analysis using SPSS 17.0 (SPSS Inc., Chicago, IL, USA). All variables were described before and after treatment. Analysis pretest and posttest values on both groups were used paired T-test and independent T-test. The statistical test results are significant if $p < 0.05$.

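### The protocol does not tie the HBOT conclusion to the between-group test or rank its three outcomes, and the paired tests under the same p < 0.05 rule cannot isolate HBOT

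*Protocol*

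**What the plan says.** All of this stands in the protocol's title and Methods.

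- **Purpose.** The title reads "Short Duration Hyperbaric Oxygen Therapy to Improve HbA1c, Leukocyte, and Serum Creatinine". The opening of the Methods gives the aim as "to know the role of standard therapy and combination therapy (standard therapy with adjuvant HBOT") in lowering the three laboratory values, which are listed as equals.
- **Groups.** Patients willing to use HBOT form the combination group. For the others, "if they are willing to participate in the study but do not want to use HBOT was grouped to standard therapy".
- **Size.** "Thirty diabetic patients with DFU Wagner 3-4 were participated in this study". The split between the groups is not given.
- **Timing.** The first blood sample is taken "before debridement, then grouped for standard therapy or standard therapy with 10 sessions of HBOT". For the second, "At the end of therapy, all blood tests were performed again in both groups". Debridement is an inclusion criterion, so every patient has it.
- **Analysis.** "Analysis pretest and posttest values on both groups were used paired T-test and independent T-test". The paragraph closes with the threshold: "The statistical test results are significant if $p < 0.05".

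The protocol does not say which of the two tests carries the HBOT conclusion, which outcome comes first, or that the between-group test takes account of the pretest value.

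**The concern.** The two tests answer different questions. A paired test asks whether a group changed between the two blood samples. An independent test asks whether the groups differ. Only the second bears on whether HBOT adds anything to standard therapy. The protocol sets them side by side under one threshold and does not assign the HBOT question to either.

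In the combination group, the change from first to second sample is the sum of debridement, the rest of standard therapy, the passage of time and any HBOT effect. A significant paired result there is expected whenever standard care works. If it is set beside a non-significant paired result in the standard group, the contrast can look like evidence for HBOT although the groups were never compared. With the outcomes unranked, it is also open which one the conclusion stands on, and that can be settled after the results are known.

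**Working it through.** **What can be reproduced.** The protocol gives no effect size, SD or power, so the total of 30 has no calculation behind it to check. The 0.05 is a per-test threshold, with no overall error rate claimed. What can be calculated is how the paired tests behave when HBOT has no effect.

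**Inputs.** From the protocol: 30 patients in total, three outcomes, threshold 0.05. Assumed: a two-sided test; 15 per group, with 20/10 and 10/20 as a range; normal changes; no HBOT effect; the same true improvement d in both groups, in SD units of the change, of 0.25, 0.5 or 0.75.

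**Step 1: the paired test in one group.** The statistic follows a noncentral t distribution with n − 1 degrees of freedom and noncentrality d√n. The probability of a significant improvement is P(T > t₀.₉₇₅,ₙ₋₁). For n = 15 the critical value is 2.145 and the noncentralities are 0.25 × √15 = 0.968, 0.5 × √15 = 1.936 and 0.75 × √15 = 2.905.

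| n in group | d = 0.25 | d = 0.5 | d = 0.75 |
|---|---|---|---|
| 10 | 0.106 | 0.293 | 0.562 |
| 15 | 0.145 | 0.438 | 0.771 |
| 20 | 0.185 | 0.565 | 0.889 |

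**Step 2: significant with HBOT, not significant without.** The groups contain different patients, so the probability is p(combination) × [1 − p(standard)]. At 15/15 and d = 0.5 this is 0.438 × 0.562 = 0.246.

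| Combination / standard | d = 0.25 | d = 0.5 | d = 0.75 |
|---|---|---|---|
| 15 / 15 | 0.124 | 0.246 | 0.177 |
| 20 / 10 | 0.165 | 0.399 | 0.389 |
| 10 / 20 | 0.086 | 0.128 | 0.063 |

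These are rates per outcome, with no HBOT effect at all. They also depend on the unstated split: a larger combination group makes the misleading pattern more likely.

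**Step 3: the between-group contrast in the same setting.** A test of posttest adjusted for pretest (15/15, assumed pre-post correlation 0.5, 100,000 simulations) was significant in 0.050, 0.051 and 0.050 of runs for the three values of d, and favoured HBOT in about 0.025. The shared improvement cancels. A plain independent t-test also holds 5% here, so error control comes from comparing the groups and not from the adjustment.

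**Step 4: what the adjustment adds.** First, precision. At a pre-post correlation r the residual SD shrinks by √(1 − r²), which is √(1 − 0.25) = 0.866 at r = 0.5. The difference detectable with 80% power at 15 per group falls from 1.06 to 0.92 SD (1.06 × 0.866 = 0.92). Second, baseline differences. If the groups differ by D at pretest and nothing else separates them, a posttest comparison is expected to show r·D and a comparison of changes (r − 1)·D with no treatment effect. The adjusted contrast removes that part. This matters because patients chose their group.

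**Step 5: the unranked outcomes.** If any one of three between-group tests counted as success, the nominal error with independent outcomes would be 1 − 0.95³ = 0.143. If all three were required it would be at most 0.05. The protocol states neither rule.

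**The case against.** The case on the other side has several parts.

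- **A between-group test is named.** The design has a control group, and the independent t-test is the only named test that compares the groups, so it is the natural candidate for the HBOT question. This stands. A reader might infer that the protocol contains no between-group comparison, and the text does not support that. What is missing is the statement that the conclusion rests on it.
- **The paired tests are legitimate.** The aim covers the role of each therapy, and a significant paired result in a group that truly improved is correct for that question. This also stands. The rates above are not false positives of the paired test. They show how often it would mislead if read as an HBOT effect, and nothing in the protocol says it will be read that way.
- **No success rule is stated.** The 0.05 applies test by test, and the three outcomes are joined as a set. A reader might infer a 14.3% overall false-positive rate, but that needs an any-one-of-three rule that the protocol does not contain. Pooling all paired and independent tests into one error rate has less support still, because it mixes different questions and assumes that neither group changes.
- **Detail may sit in a statistical analysis plan that is not shown.** That is fair for a multiplicity rule, whose absence is not held against the protocol. But the protocol does state an analysis, and the one it states can be improved with data already collected.
- **The title may express purpose, not result.** Agreed. Nothing here depends on reading it as a claim.

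**Conclusion.** The point holds in a limited form and is a cheap improvement. The protocol applies paired and independent t-tests to three unranked outcomes under one threshold, does not rest the HBOT conclusion on the between-group test, and names that test without adjustment for pretest.

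If the combination-group paired result were taken as evidence for HBOT, it would mislead in about 15% to 77% of trials per outcome over the shared improvements considered. The contrast of one significant and one non-significant paired test would mislead in about 12% to 25% at 15 per group, and in 6% to 40% across the splits tried. The group sizes and shared improvements are assumptions, since the protocol gives only the total. The 5% for the between-group contrast is nominal, because it supposes groups that do not differ systematically, and these were formed by patient choice.

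The documents do not support saying that an HBOT comparison is absent, that the paired tests are wrong for their own purpose, or that a particular overall error rate applies.

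**What to change.** Add two or three sentences to the statistical paragraph:

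1. The conclusion about HBOT rests on one between-group contrast per outcome, posttest adjusted for pretest, reported with a confidence interval.
2. The paired tests describe change within each group and carry no conclusion about HBOT.
3. One named outcome is primary, and the other two are supportive.

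Parts of the Methods are in the past tense. If the data have been seen, label all three choices post hoc, including the adjusted model.

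The cost is one linear model per outcome on values already measured. The threshold for the primary outcome stays at 0.05, and at an assumed pre-post correlation of 0.5 the adjustment gains precision. The price is that two of the three outcomes become supportive. The adjusted contrast can reduce bias that runs through pretest differences, but it does not remove bias from patients choosing their group, and the report should say so.
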